5.4 Withdrawal from the study

A patient may be withdrawn from the study if any of the following events occur:

- If, in the opinion of the investigator, withdrawal is necessary for medical or technical reasons
- Major protocol violation
- Informed consent withdrawal

In case of a withdrawal before first treatment day, another patient will be enrolled (with a new patient number). The withdrawn patient will be accounted for in the statistical analysis. The reason for withdrawal should be clearly described. Relevant data should be obtained when possible, and all relevant assessments should be completed, preferably according to the schedule for the final assessment. The eCRF should be completed.

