6.4 Esophagus sparing radiotherapy vs. standard treatment

For the patients in the standard arm, a standard radiotherapy plan computed using VMAT technique aiming at covering the PTV with at least 90 % of the prescribed dose and not taking the dose to the esophagus and/or stomach into account.

For the patients in the interventional arm, a plan using VMAT technique is computed aiming at keeping the maximum dose to the esophagus and/or stomach as described in Table 4. Even if it means compromising the dose to the PTV and CTV.

Patients randomized to esophagus sparing radiotherapy needing reirradiation (**other target that primarily prescribed**) during the 9 weeks of FU, will receive esophagus sparing radiotherapy for the second target.

	Maximum Physical Esophageal Dose ($D_{0,027\text{cm}^3}$) (Gy)		Max. Esophageal Dose in EQD2 ($D_{0,027\text{cm}^3}$) (Gy), $\alpha/\beta = 3$ Gy	
Fractionation (Dosis (Gy) x Fraction)	Standard arm	Esophagus sparing arm	Standard arm	Esophagus sparing arm
5 Gy x 5	25	8,5	40	8
3 Gy x 10	30	10	36	8
10 Gy x 1	10	5	26	8
8 Gy x 1	8	5	17,6	8

Table 4. Maximum esophageal dose. Standard arm vs. esophagus sparing arm.

7 HbA_{1c} and Flash glucose monitoring

HbA_{1c} will be measured at baseline, which is standard procedure in one of the participating centers.

²³ In order to obtain ambulatory glucose profiles for retrospective glucose data analysis we will use a blinded professional sensor-based Flash glucose monitoring system (FreeStyle Libre Pro™; Abbott Diabetes Care, Witney, UK).^{19,20} The sensor is worn on the upper arm for 14 days. The sensor is factory calibrated which means that, after activating the sensor at baseline, no further intervention during the 14-day wear is required. As the sensor is blinded, data are not visible to participants or investigators during sensor wear. The sensor automatically captures and stores glucose data every 15 min (96 glucose readings/day). After 14 days the sensor is dismantled, and glucose data are wirelessly transferred to the pro-reader. Summary glucose reports are generated using the system software. Patients in our study will be followed for 28 days after start of radiotherapy treatment requiring one sensor change. This will include time without glucocorticoid treatment.

The patients participating in this part of the study will not be subject to standard glucose measurements; instead they will be thoroughly instructed to contact the PI if symptoms of hyperglycaemia should occur.

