Data are reported by the patient in a paper-edition trial diary, by electronic questionnaires or by telephone consultations. Survival data, re-irradiation, and hospitalization data are derived from patient's treatment records. After the results of an interim analysis revealing low compliance (1), weekly CTC registrations were implemented for all patients in the first 5 weeks after treatment start (from patient No. 107).

Table 1. Follow-up schedule in the ESO-SPARE trial

	Treatment start	Daily	Weekly	Weekly
		1-5 weeks	1-5 weeks	1-9 weeks
PRO-CTC-AE: Dysphagia, nausea, dyspepsia	X	X		
CTC-AE 5.0*	X		X	
EORTC-QLQ-C30 and EQ-5D-5L	X			X
Medication: Analgesics, corticosteroids, antiemetics	X			
Weight	X			X

*Starting from patient No. 107

Estimated Enrollment: 200 patients.

Allocation: Patients are randomized 1:1 to either esophagus-sparring treatment or standard treatment. Patients are stratified by center and fractionation. Randomization is performed in REDCap using random allocation with a block size of four and six.

Masking: Single-blind. Patients are blinded to randomization outcome.

Study Start Date: May 2021

Estimated Primary Completion Date: April 2024

Study Completion Date: The last patient will be included on April 30, 2024, or after the inclusion of 200 patients, whichever comes first.

Timing of final analysis

Following study closure, nine weeks of follow-up after radiotherapy start will be allowed for all patients, at which point data will be collected for primary end-point analysis. Analysis of data in respect to secondary endpoints and exploratory studies might be analyzed at any point of time, at the discretion of the study group.

Data

Data are captured in REDCap. Data will be kept in databases 10 years after the last patient is included.

[Sample size](#)

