Table 2: Distribution of ambulatory function. The conventional arm follows the SCORAD trial (Hoskin et al., 2019).

Recruitment, withdrawal, and follow-up

Enrollment, intervention, allocation, follow-up, and data analysis will be summarized in a CONSORT diagram in accordance with CONSORT 2010 guidelines (4)

Statistical principles

Confidence intervals and P values

Level of significance: $p < 0.05$ with no adjustment for multiplicity. Confidence intervals are reported at 95 % limits (bound by zero) and calculated by the binominal distribution for rates and as per Kaplan-Meier method for time-to-event analyses.

Analysis

We will report our data in accordance with the CONSORT 2010 guidelines including the CONSORT Patient-Reported Outcome (PRO) extension (4,5) .

Analyses will be performed per-protocol for all patients who have received any study treatment.

Primary analysis of NCI-PRO-CTC-AE toxicity will only include weeks where ≥ 3 days questionnaires are completed.

Primary analysis of EQ-5D-5L and EORTC-QLQ-C30 will only include completed questionnaires.

All CTC-AE and PRO-CTC-AE grades will be reported.

Missing data will be described in detail, see missing data section.

A. Co-primary endpoints

1. Peak dysphagia (difficulty swallowing) measured by NCI-PRO-CTC-AE within 5 weeks after start of radiotherapy (daily measurements).

PRO-CTC-AE responses are scored from 0 to 4, with 0 representing "None" and 4 representing "Very severe". For each patient the peak value within 5 weeks after start of radiotherapy (daily measurements) will be included in the analysis. Difference in scores between treatment arms will be compared using Wilcoxon rank-sum test.

2. Ambulatory function measured by EQ-5D-5L mobility dimension at 9 weeks after start of radiotherapy.

EQ-5D-5L measures individual generic health status using 5 dimensions: mobility, self-care, usual activities, pain/discomfort, and anxiety/depression. Each dimension has 5 levels depending on the severity of symptoms, with 1 representing “No problems” and 5 representing “Extreme problems”. Difference in scores between mobility dimension treatment arms will be compared using Wilcoxon rank-sum test.

B. Severity of dysphagia, nausea and dyspepsia measured by NCI-PRO-CTC-AE [Time Frame: Week 1-9 after start of radiotherapy (repeated measurement)].

CTC-AE responses are scored from 0 to 4, with 0 representing “None” and 4 representing “Very severe”.

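### The SAP's analysis-set sentence joins two different sets (per-protocol and all-treated), and neither co-primary endpoint has a stated analysis by allocated arm

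*SAP*

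**What the plan says.** The SAP, under Analysis, gives one rule that selects patients by treatment or adherence: "Analyses will be performed per-protocol for all patients who have received any study treatment". The rules beside it concern data completeness. PRO-CTCAE weeks count only if at least three daily questionnaires were filled in, and "Primary analysis of EQ-5D-5L and EORTC-QLQ-C30 will only include completed questionnaires". Both co-primary tests are Wilcoxon comparisons between treatment arms. The SAP does not say whether that means the arm allocated or the treatment received.

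Protocol 5.4 allows withdrawal on three grounds: consent withdrawn, a major protocol violation (not defined), or "If, in the opinion of the investigator, withdrawal is necessary for medical or technical reasons". It then says "The withdrawn patient will be accounted for in the statistical analysis", without saying in which arm or set. It also says "Relevant data should be obtained when possible, and all relevant assessments should be completed" and "The eCRF should be completed". A patient withdrawn before the first treatment day is replaced by a new one.

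On blinding, the SAP (Trial design) says "Single-blind. Patients are blinded to randomization outcome". Planning differs by arm under Protocol 6.4: "For the patients in the interventional arm, a plan using VMAT technique is computed", with the esophageal dose limit expressed as an aim.

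**The concern.** A per-protocol set and a set of all treated patients are not the same. Without a list of deviations, a reader cannot know before the analysis whether a patient treated with another technique, or above the dose limit, is kept. If per-protocol is applied literally, the decision falls after randomisation and could be made by staff who know the arm.

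This matters most for walking. The SAP's sample-size text treats a deterioration in walking as grounds for rejecting the sparing technique, so a result with no significant difference favours the experimental arm. The choice of set can therefore affect whether harm is seen. For dysphagia, selective removal from the sparing arm could produce an apparent benefit.

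**Working it through.** **1. Do other passages settle the set?**
- Towards keeping everyone treated: the SAP's radiation section compares delivery technique between arms, naming techniques other than VMAT, and reports esophageal volume above the constraint. The Missing data section gives reasons for missing data by arm for all randomised patients. Patients with such departures therefore seem meant to stay in their arm.
- Towards removing deviators: only the term per-protocol itself.
- Neutral: the questionnaire rules and the rule on second entries limit which records are used, not which deviations count. The optional sensitivity analysis concerns missing data only. Intention-to-treat is mentioned once (Protocol 1.2), about the cited SCORAD trial.

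The set remains open, with the weight towards a benign intent. Patients never treated fall outside it on either reading.

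**2. The plan's own figures.** Exact two-sided Fisher power for 0.6 against 0.3 with 62 per arm is 0.910 (stated: 0.9). Simulated tie-corrected Wilcoxon power for SAP Table 2 (22/44/26/8 against 11/32/37/20) with 66 per arm is 82.9% (stated: 84%). Both are close. Neither depends on the analysis set.

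**3. Walking, in two directions.** Let f be the share of the sparing arm affected. The documents give no value, so 5, 10 and 15% are assumed.

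*(a) Removed patients walk worse than average.* Retained distribution = (arm distribution − f × removed distribution) / (1 − f). For f = 0.10 with all removed patients at grade 3–4, grades 3–4 go from 57% to (0.57 − 0.10)/0.90 = 52.2%. If 80% of them are grade 3–4, the figure is (0.57 − 0.08)/0.90 = 54.4%. Control n = 66; sparing n = 66 × (1 − f), rounded to 63, 59 and 56.

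*(b) Deviators have control-arm outcomes and the others follow Table 2.* As allocated, the sparing distribution is (1 − f) × sparing + f × control. For f = 0.10 this is 12.1/33.2/35.9/18.8%, n = 66. After removal it is Table 2 again, with the smaller n.

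| Power to detect the Table 2 harm | f = 5% | f = 10% | f = 15% |
|---|---|---|---|
| (a) removed: 80% grade 3–4 | 78% | 73% | 66% |
| (a) removed: 100% grade 3–4 | 75% | 64% | 52% |
| removed: arm average (57%) | 82% | 81% | 80% |
| (b) kept as allocated | 79% | 74% | 69% |
| (b) deviators removed | 82% | 81% | 80% |

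Under (a) removal hides harm; under (b) keeping the patients dilutes it. Table 2 has four grades and the EQ-5D-5L mobility item has five, so these figures are illustrations.

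**4. Dysphagia with no true effect.** Assumptions: any-toxicity rate 0.60 in both arms, 100 per arm, the SAP's Wilcoxon test at two-sided 0.05, and three assumed 0–4 distributions (40/25/20/10/5, 40/40/12/6/2 and 40/15/20/15/10%). If 10% are removed at risk 0.9, the retained rate is (0.60 − 0.09)/0.90 = 0.567.

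| Two-sided rejection | f = 5% | f = 10% | f = 15% |
|---|---|---|---|
| removed at average risk (0.6) | about 5% | about 5% | about 5% |
| removed at risk 0.8–0.9 | 5.2–5.5% | 5.8–7.1% | 7.1–10.2% |

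With nobody removed the figure is 5.0–5.1%. Inflation therefore depends on the removed patients differing in risk from the rest of their arm.

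**5. Cost of analysis as allocated for dysphagia.** If 5, 10 or 15% of the sparing arm have the control rate and stay in their arm, Fisher power with 100 per arm goes from 0.99 to 0.98, 0.97 and 0.95.

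**The case against.** The strongest reply is that, with no deviation list, the only workable criterion in the sentence is having received any study treatment. The SAP defines the arms by randomisation, and its radiation and missing-data sections expect departures to be reported within arms. That stands. A reader might infer that an analysis by allocated arm has been ruled out, or that deviators will be dropped. The documents support neither: such an analysis is only unstated, and Protocol 5.4 asks for withdrawn patients' data and removes nobody from the analysis.

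A second reply is that removal need not flatter the sparing arm. The protocol accepts that sparing may compromise target dose. A patient over the esophageal limit may therefore have had fuller target dose and may walk better, and removing such patients would expose harm. That also stands, and case (b) shows it. It counts equally against assuming that analysis as allocated is the cautious choice for walking.

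Third, no documented rule would remove high-risk patients, so the inflated dysphagia figures have no stated mechanism. That is right; they show sensitivity, not expectation. Fourth, the planned CONSORT diagram and the missing-data counts by arm should show afterwards who was analysed. That helps reporting, but it does not fix the set in advance.

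**Conclusion.** The ambiguity is certain; its effect is not. On the likelier reading, treated patients analysed in their allocated arm, the label is wrong and bias should be small. On the literal reading, removal after randomisation by staff who know the arm is permitted and its criteria are undefined. Because no exclusion rate is documented, neither size nor direction can be given. Under the assumed 5–15%, power to detect the tabled walking harm ranges from 82% down to 52%, depending on who is removed or kept, and removal can either hide harm or reveal it. A reader might conclude that the co-primary results are biased towards sparing; the documents do not support that. The point should be fixed because a definite rule is cheap and a safety-type comparison depends on it.

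**What to change.** Replace the sentence in the SAP's Analysis section with:

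> Both co-primary endpoints are analysed primarily in the arm allocated, whatever plan or dose was delivered, in all randomised patients with evaluable data under the stated questionnaire rules (at least 3 days per week for PRO-CTCAE; completed EQ-5D-5L). Patients withdrawn under Protocol 5.4 stay in their allocated arm with the data obtained. Randomised patients without evaluable data, including those withdrawn before treatment and replaced, are counted by arm with the reason. A per-protocol set, with exclusion criteria listed before the analysis, is a sensitivity analysis, and both sets are reported for walking, where no difference favours the experimental arm.

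The counts fit the CONSORT diagram and the missing-data report already planned. The cost is a few sentences and a little more analysis, with no new patients or data. The estimated benefit may be slightly less favourable.

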2.1 Primary endpoint

- Early patient reported gastro-oesophageal toxicity measured as peak score within the first 5 weeks after treatment start measured by PRO-CTCAE, see Appendix A.

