3.6 Time frame

ESO-SPARE- Esophagus-sparring radiotherapy: 200 patients will be enrolled within a timeframe of maximum of three years. The study will close after three years regardless if the planned number of

enrolled patients is reached or not. Accrual and compliance will be assessed after inclusion of the first 50 patients. If compliance falls below 50% in more than 1/4 of patients, accrual will be extended to 250 patients. If compliance falls below 50% in more than ½ of patients, accrual will be extended to 300.

Compliance is defined as the patient's ability to answer at least half of the daily questionnaires within the first two weeks.

GLUC-DIAB - Glucocorticoid-diabetes: 150 patients will be enrolled within a timeframe of maximum of three years. The study will close after three years regardless if the planned number of enrolled patients is reached or not.

4 Visits and follow-up procedure

Patients will be scheduled for follow-up according to Table 2. Additional imaging or laboratory investigations are at the discretion of the treating oncologist. Inclusion of patients and recording of baseline data will take place when the patients come for the planning procedures for radiotherapy. Follow-up may be done electronically or using paper edition questionnaires. Paper edition questionnaires may be returned in relation to another hospital visit or by mail. Registration will be obtained from the patient's electronic records after they have signed informed consent. The clinical information registered will include age, sex, height, weight, smoking history, medical and surgical history, all medicine, performance status, pathology, type of systemic treatment, scan results, radiotherapy dose and schedule, further irradiation including re-irradiation. Patients will be followed till death but will only actively be followed for 9 weeks.

	Baseline	EOT	Daily Week 1-4 after start of RT	Daily Week 1-5 after start of RT	Weekly Week 1-5 after start of RT	Weekly Week 6-9 after start of RT
Signed consent	x					
Performance status	x					
Weight*	x	x			x	x
Registrations of analgesic, steroids, antacids and antidiabetic medication	x	x			x	x
EuroQol EQ-5D-5L Index*	x				x	x
EORTC QLQ-C30*	x				x	x
PRO Gastro-oesophageal symptoms*	x			x		x
PRO pain incl. numeric pain rating scale*	x			x		x
HbA _{1c}	x					
Flash glucose measurements			x			

Table 2 Schedule for visits and follow-up procedure. *Electronic questionnaire or telephone questionnaire

Quality of life

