We assume that we can decrease maximum esophageal dose from 30 Gy to 10 Gy and that this will result in a 50% decrease in risk of early esophageal toxicity. We want to conduct a phase III trial with 1:1 randomization between standard VMAT and experimental esophageal VMAT. Prior data (2) indicate that the rate of early esophageal toxicity with standard VMAT is 0.6. If the true early esophageal toxicity rate in the esophagus sparing VMAT arm is 0.3, conventional power calculation indicates that we would need to include 62 patients in each arm, to be able to reject the null hypothesis that the toxicity rates for experimental and control arms are equal with a probability (power) of 0.9. The Type I error probability associated with the test of this null hypothesis is 0.05 and calculations are performed assuming Fisher's exact test. However, with this patient population we anticipate high rate of heterogeneity, and we need to account for loss of follow-up due to patients dying early or being too frail. We increase the study size to 100 patients in each arm to account for these challenges. Patients will be stratified according to fractionation scheme and treating center.

Ambulatory function as a co-primary endpoint

We wish to demonstrate that the improvement in esophageal toxicity does not come at a price of reduced effect of the radiation. As a prioritized secondary endpoint, we choose ambulatory function (preserved ability to walk) measured on a 4-point scale. We assume that the conventional arm follows the distribution of the SCORAD trial and test our ability to detect a difference from an assumed inferior experimental arm in terms of ambulatory function, see Table 2.

If the underlying “true” distribution on ambulatory grades is as depicted in the table and we assume 66 patients per arm are evaluable, we find that 84% of simulated trials would lead to statistically significant differences detected with a Wilcoxon rank sum test for comparing the trial arms. In other words, the power of the trial is enough to detect a deterioration according to the able, which would lead to rejection of the experimental treatment.

The power of ESO-SPARE is enough to detect a difference in ambulatory function as seen in Table 2

	Conventional arm	Experimental arm
Grade 1: Ambulatory without the use of walking aids	22	11
Grade 2: Ambulatory with walking aids	44	32
Grade 3: Unable to walk	26	37
Grade 4: Absence or flicker of motor power in any muscle group	8	20

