For each of the first five weeks, where daily measurements are recorded, the peak value will be used for analysis. Changes in severity score over time (repeated measurement) will be analyzed using Generalized Linear Mixed Models.

C. Duration of dysphagia, nausea and dyspepsia measured by NCI-PRO-CTC-AE [Time Frame: within five weeks after start of RT (daily measurements) and at 6, 7, 8, and 9 weeks].

Duration of toxicity will be presented graphically in separate figures.

For the first five weeks mean duration (days) in each group will be compared using Wilcoxon rank-sum test.

D. Severity of cough, oropharyngeal pain, dyspnea, dysphagia, hoarseness, and dyspepsia measured by CTC-AE (weekly measurements) [Time Frame: Week 1-5 after start of radiotherapy (repeated measurement)].

CTC-AE responses are scored from 0 to 4, with 0 representing “None” and 4 representing “Very severe”.

Changes in severity score over time (repeated measurement) will be analyzed using Generalized Linear Mixed Models.

E. Duration of cough, oropharyngeal pain, dyspnea, dysphagia, hoarseness, and dyspepsia measured by CTC-AE (weekly measurements) [Time Frame: Week 1-5 after start of radiotherapy (repeated measurement)].

Duration of toxicity will be presented graphically in separate figures. Mean duration (weeks) in each group will be compared using Wilcoxon rank-sum test.

F. Demographics: Subject demographics, baseline characteristics and medical history will be summarized descriptively. Generally, range, mean and standard deviation, or median and inter quartile range, will be reported for continuous variables. Frequencies and proportions will be reported for categorical variables.

G. Treatment site pain response [Time frame: weekly, 1-9 weeks after start of RT]:

Only patients with baseline pain will be included in the analysis.

Pain response will be measured by the ICPRE score (6). Possible responses are “Complete response”, “Partial response”, “Pain Progression” and “Intermediate response”.

For each of the first five weeks, where daily measurements are recorded, the worst response will be used for analysis. Changes in ICPRE score over time (repeated measurement) will be analyzed using Generalized Linear Mixed Models.

H. Duration of treatment site pain response [Time Frame: Weekly week 1-9 after start of radiotherapy].

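### The SAP's three-forms-per-week filter, as written, also removes observed high scores from the 5-week peak dysphagia co-primary

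*SAP*

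**What the plan says.** The SAP's Analysis section opens with general rules that stand ahead of analyses A to O. One of them reads "Primary analysis of NCI-PRO-CTC-AE toxicity will only include weeks where ≥ 3 days questionnaires are completed". The first analysis beneath, A.1, is the dysphagia co-primary: one NCI-PRO-CTC-AE item scored 0 to 4, tested by Wilcoxon rank-sum, for which "For each patient the peak value within 5 weeks after start of radiotherapy (daily measurements) will be included in the analysis". A.1 neither repeats nor waives the week rule. Protocol 2.1 has the endpoint "measured as peak score within the first 5 weeks after treatment start measured by PRO-CTCAE", with no minimum number of forms.

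Analysis B uses one value per week: "For each of the first five weeks, where daily measurements are recorded, the peak value will be used for analysis". A week filter fits there naturally.

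Other text bears on the point. The same general rules promise "All CTC-AE and PRO-CTC-AE grades will be reported". The Missing data section allows, but does not require, multiple imputation and missing-not-at-random models. The Sample size section says "we need to account for loss of follow-up due to patients dying early or being too frail". Protocol 3.6 defines compliance as the patient's "ability to answer at least half of the daily questionnaires within the first two weeks". The SAP's Trial design section reports that an interim analysis found low compliance, but gives no rate.

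**The concern.** A.1 is a maximum. Each observed score is a lower bound for the patient's true peak, however few other forms were filled in that week. A rule that removes observed days can therefore lower the analysed peak or leave it unchanged, never raise it.

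Take a patient who scores 0 or 1 in four qualifying weeks and 4 on the single form of week 3. The protocol's definition gives a peak of 4; the SAP's rule gives 1.

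A minimum-data rule is reasonable in itself, because a patient who stops after two forms should not count as free of dysphagia. The fault is narrower: the rule also deletes scores of patients who are otherwise evaluable.

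With equal completion in both arms this lowers the observed toxicity rates and dilutes the difference. With unequal completion, peaks are lowered more in one arm, which can create a difference or hide one.

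**Working it through.** **1. The plan's own figure.** Inputs from the SAP's Sample size section: toxicity 0.6 v 0.3, alpha 0.05 (taken as two-sided, since sidedness is not stated), power 0.9, Fisher's exact test. Exact enumeration gives power 0.902 at 61 and 0.910 at 62 per arm, so 62 is supported. The week filter plays no part in that calculation.

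**2. An anchor from the protocol.** Take a patient who completes exactly 7 of the 14 forms in weeks 1–2, and so just counts as compliant under Protocol 3.6. If the forms fall at random, the chance that a given week holds 0, 1 or 2 of them is

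[C(7,0)·C(7,7) + C(7,1)·C(7,6) + C(7,2)·C(7,5)] / C(14,7) = (1 + 49 + 441)/3432 = 0.143.

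Both weeks cannot fail together, so the chance that one of them fails is 2 × 0.143 = 0.286, or 29%.

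**3. Weeks that hold data but are dropped.** With independent days and completion probability p, this is P(1 or 2 forms) = 7p(1−p)^6 + 21p²(1−p)^5. At p = 0.5 it is (7 + 21)/128 = 0.219. If completion varies between patients, a beta-binomial with a + b = 4 is used instead. Both are in the table below.

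**4. Effect on the test.** Simulation of 35 daily scores, 100 patients per arm, true toxicity 60% v 30%, Wilcoxon two-sided 0.05, 2000 trials per setting. Assumptions:
- onset on days 8–16 and duration of mean 11 days (SD 4, limited to 1–18), guided by the pilot in Protocol 1.2;
- peak grades 1/2/3/4 in 40/35/20/5% of toxic patients;
- ranges run over common or patient-varying completion and over flat or rise-and-fall episodes.

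The alternative keeps the same evaluable patients (at least one week with three forms) but takes the peak over all their completed days.

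| Daily completion | Weeks with data dropped (independent / varying) | Evaluable patients with observed dysphagia analysed below their observed peak | Power, rule | Power, alternative |
|---|---|---|---|---|
| 30% | 57% / 40% | 20–37% | 0.75–0.83 | 0.87–0.96 |
| 40% | 39% / 35% | 15–21% | 0.88–0.94 | 0.94–0.98 |
| 50% | 22% / 27% | 6–13% | 0.94–0.98 | 0.96–0.98 |
| 60% | 9% / 18% | 2–8% | 0.97–0.99 | 0.98–0.99 |
| 70% | 3% / 11% | 0–5% | 0.97–0.99 | 0.98–0.99 |

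At 40% completion the observed toxicity rates are 49–50% v 25% under the rule and 58% v 29% under the alternative. With equal completion and no true effect, the false-positive rate is 0.04–0.06 for both.

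**5. Completion differs by arm (assumption).** With no true effect (45% toxicity in both arms, 4000 trials), false positives are 0.09–0.18 under the rule v 0.05–0.06 at 60% v 40% completion, and 0.06–0.08 v 0.05 at 55% v 45%. With a real effect and less reporting in the control arm (40% v 60%), power is 0.76–0.82 v 0.95–0.98.

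**6. Completion falls with severity (assumption).** With 50% baseline completion and a logit change of −0.5 per grade, power is 0.84–0.92 v 0.94–0.98. At −1 per grade it is 0.58–0.74 v 0.86–0.95.

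**7. Early stopping.** If 10% v 30% stop within the first 2, 3 or 7 days and there is no true effect, false positives are 0.05–0.16 under both the rule and the alternative, but 0.12–0.26 for an unrestricted peak over all days in everyone with a form. Over all stopping times tried, up to day 35, the alternative was never more than 0.01 above the rule. If 30% stop in both arms and the effect is real, power is 0.71–0.90 v 0.81–0.96 at 40% completion and 0.88–0.97 v 0.90–0.97 at 70%.

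**The case against.** The strongest reply is that the filter was meant only for the weekly peaks of analysis B. A.1 is the more specific text and, read alone, uses all daily values. Read literally everywhere, the filter would also empty weeks 6–9 of analysis B, where there is one form per week. That reading is plausible, but the SAP does not state it. The filter names the primary analysis of the instrument, and A.1 is the primary endpoint on that instrument. Two analysts could derive different co-primary values from the same data.

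The second reply is about size. Protocol 3.2 and 3.6 extend accrual to 300 if more than half of patients answer under half the forms in weeks 1–2. Under the two completion models above, only 9–24% of patients reach half at 30% completion and 31–39% at 40%, so either should have triggered 300. The SAP, written after the interim analysis, still plans 200, which would suggest about 55–65% completion, where the loss is small. This is an inference only: the extension may not have been applied, Protocol 3.6 also closes the study after three years whatever the accrual, weeks 3–5 may be worse, and the SAP itself calls compliance low.

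Third, even at 40% the rule's power is close to the planned 0.90, and a simpler simulation with constant completion and fixed 11-day episodes gives 0.95. But these figures use all 100 patients per arm, whereas the 38 beyond 62 were added for heterogeneity and loss to follow-up.

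Fourth, no document shows that completion differs by arm, and patients are blinded. That stands, so the false-positive figures are conditional.

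Finally, weekly clinician-graded dysphagia was added from patient 107. It is a second measure but does not enter A.1. Nor do descriptive reporting of grades or optional imputation put a discarded score back into the tested value.

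**Conclusion.** The concern holds. As written, the week filter covers co-primary A.1 and departs from the protocol's definition of the peak by discarding scores that patients actually gave. The direction within a patient is certain: the peak is lowered or unchanged.

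The size is not known, because the documents give no completion rate. With equal completion the power loss is material at about 30–40%, small at 50% and negligible from about 60–70%. Inflated false positives require completion to differ by arm, and are slight for a 10-point gap. All power figures rest on the assumed episode timing, duration and grade mix. The stated 62 and 100 per arm do not change. This should be corrected because it concerns a co-primary endpoint and is cheap to settle.

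**What to change.** Before the arms are compared, state in the SAP that:
- for A.1 the three-form rule decides only whether a patient is evaluable, meaning at least one of weeks 1–5 has three or more completed forms;
- the peak of an evaluable patient is the highest score on any completed day in weeks 1–5;
- the weekly filter stays for the week 1–5 peaks in analysis B, and not for weeks 6–9.

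Pre-specify three sensitivity analyses: (a) the peak from qualifying weeks only, as now worded; (b) the all-days peak in every patient with at least one form; (c) the corrected peak only in patients with a qualifying week 2 or 3. Report by arm the completed days per week and the patients without a qualifying week. The unrestricted peak in (b) should not be primary, because early stoppers would score near 0.

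The cost is a change of wording and one re-derived variable; no new data are needed. Patients without a qualifying week stay excluded, as now: of those who reported, 11–34% at 30% completion, 1–20% at 40%, 0–11% at 50% and 0–2% at 70%. The peak still depends partly on how many days were completed, and bias from stopping in weeks 1–2 that differs by arm remains. Analysis (c) brought that false-positive rate to 0.04–0.06, but only because onset was assumed in weeks 2–3. That timing comes from a 10-fraction pilot, and the documents give none for 1 or 5 fractions.
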